## Methods

### Trial Design

We will perform a randomized parallel trial in a single highly trained female soccer team (highly trained/national level) (McKay et al., 2022) competing in the Portuguese second division. A convenience sample will be used, due to easy access from one of the researchers, who is employed in the club. One group will receive the experimental intervention (EXPG), which will consist of a potentiation protocol as a WU and the second group will receive the control intervention (CONG) which consists of performing their usual WU exercise program. Each group will be tested before and after performing the WU to which they are assigned. Physical tests and intervention protocol will take place during the competitive period. All training sessions and physical tests will be performed on synthetic grass of the team's field. The tests will be applied without a blinded assessor integrating the technical team. However, due to the use of objective and reliable technology, hardly influenced by knowledge of the interventions to which the participants were allocated, we are confident that the non-blinded of assessors will not have a meaningful impact on the results.

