## Participants

Eighteen female soccer players between 16 and 21 years of age will participate in this study. Participants will be randomly allocated between a CONG (n=9) and a EXPG (n=9), using the Excel Software and the Random function and the allocation sequence will be concealed from the main researcher, responsible for the implementation of the protocols, until the beginning of the interventions. The inclusion criteria, to be applied before the randomization process, will consider athletes, from any playing position (except goalkeepers), able to train without limitations. Subjects will be excluded if they have any existing medical conditions that will compromise their participation. All participants will be informed about the purpose and content of the project, as well as the potential risks and benefits of the study, and will sign an informed consent.

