## Interventions

We have stipulated that the intervention will last three weeks. The first week will be a week of familiarization with the physical tests and protocol, requiring two training sessions, before the initiation of the study to accustom themselves to the physical tests and the protocol procedures. During the first week, the familiarization with the physical tests and the protocol will be performed before the training sessions. The protocol intervention will be performed in the following two weeks, in a total of four training sessions (two per week). The collection of data from the physical tests will begin in the second week, the first moment of collection will be at the at the beginning of first training session and the second moment at the end of the third week (after the fourth protocol session has been completed). The duration of each session will be 20 min.

The intervention protocol proposed in the present study was modified from the protocol used by Aloui et al. (2021), and consists of four sets: (i) First set - 6 hurdle jumps (HJ), with a

distance of 70-cm between each, followed by a 15-m sprint with COD; (ii) Second set - 6 lateral HJ (3 to the left and 3 to the right) followed by a 10-m sprint with COD; (iii) Third set - 6 bouncy strides (BC) followed by a 15-m sprint with COD; (iv) Fourth set - 6 broad jumps (BJ) followed by a 10-m sprint with COD. All COD circuits represent different configurations, changing the sprint distance and the angle of the COD curve. In the last set, we replaced the drop jump with the BJ. Due to the drop jumps being done consecutively, there is a component of horizontal resistance, so we chose to implement the BJ, which offers a greater horizontal component (Dello Iacono et al., 2017) and the forces are generated in the same musculature across the hips, knees, and ankles (Svantesson & Grimby, 1995), being a precursor exercise to improved performance in the sprint and COD (Dello Iacono et al., 2017). All repetitions and sets will be separated by 90-s recovery intervals, as well as, each set will have to be performed 3 times (Aloui et al., 2021). It should be noted that it is intended that the participants perform the procedures under study at the same time of day, i.e., same time and temperature as similar as possible. All physical tests and protocol under study are to be performed with the participants wearing their usual soccer shoes.

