## Outcomes

### T-test

Pre-planned COD will be assessed through the T-test (Krolo et al., 2020), and applied according to standardized procedures described elsewhere (Miller et al., 2006). However, forcing the participant to touch on each cone is not uniform (Raya et al., 2013), and this step will be withdrawn. We will implement course directions used previously (Miller et al., 2006). The validated and reliable WICHRO® Wireless photocell system (Chronojump®), which consists of two pairs of barriers containing the photocell and its double reflector, will be used (López-Samanes et al., 2020), and the test will start and end on the same pair of barriers. Each player will perform each test once due to the time limitation for collecting the test data.

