### 40-m linear sprint

The same WICHRO® Wireless photocell system will be used for the 40-linear sprint (Iruetia et al., 2022). The time will be counted in seconds and thousandths of a second (ms) with an error of  $\pm 0.001$ s (Sánchez-Pay et al., 2021). After a 5 s countdown, the participants run forward following the route marked by cones, one at 0m indicating the start place and the other at 40m indicating the finish place. Participants will start the test from a standing start position with the front foot approximately 2 cm behind the first cone.

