### Statistical analysis

An intention-to-treat analysis will be performed. The normal distribution will be verified by the Shapiro-Wilk test. The statistical analysis will involve descriptive and inferential statistics, and data will be presented by mean  $\pm$  standard deviation. Then, a mixed repeated measures ANOVA (i.e., within- and between-factors) will be used. The assumption of sphericity will also be analyzed. Effect sizes will be calculated using partial eta squared ( $\eta_p^2$ ) and will be classified as small (0.010-0.059), moderate (0.060-0.137), and large ( $>0.137$ ) (Cohen, 2013). Statistical significance will be assumed at  $p < 0.05$ . Statistical analysis will be performed using the IBM SPSS (*Statistical Package for the Social Sciences*) version 27.

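### A low-cost improvement, not an error: adjusting post-test times for pre-test times would keep the error rate near 5% for the allocation actually obtained, which the planned mixed ANOVA does not do

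*Combined protocol and SAP*

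**What the plan says.** The Statistical analysis section gives one inferential model: "a mixed repeated measures ANOVA (i.e., within- and between-factors) will be used". It mentions no adjustment of the post-test for the pre-test, and it does not name the term that decides the result. The hypothesis at the end of the Introduction compares the potentiation protocol with the control warm-up, so group-by-time is the relevant term.

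Under Participants, "Participants will be randomly allocated between a CONG (n=9) and a EXPG (n=9"; no stratification or matching is described. The Interventions section sets two collection moments, one at the start of the first session in week 2 and "the second moment at the end of the third week". Trial Design says "Each group will be tested before and after performing the WU to which they are assigned", which could also be read as testing around the warm-up on each occasion.

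Several statements bear on the pre-post correlation, although no value is given. The T-test section says "Each player will perform each test once due to the time limitation for collecting the test data", which tends to lower it. A familiarisation week ("The first week will be a week of familiarization with the physical tests and protocol"), the intention that "participants perform the procedures under study at the same time of day", and photocell timing ("The time will be counted in seconds and thousandths of a second") tend to raise it.

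**The concern.** A change score subtracts the whole pre-test difference, as if a player 0.1 s slower at pre-test were expected to be 0.1 s slower at post-test. Unless ρr = 1, that is too much or too little, and part of a chance pre-test difference is left in the estimated effect. When ρr is below 1, the remainder favours the group that started slower; above 1, it favours the group that started faster.

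With nine players per group, visible pre-test differences are likely. Only one allocation will occur, and readers will see its pre-test means. If the groups differ clearly, the planned p-value and any interval built on it do not have their nominal properties for that allocation. Choosing an adjusted model only after seeing the imbalance would raise a further doubt, which stating it in the plan avoids.

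**Working it through.** The plan gives no SD, correlation, effect size or power figure, so there is no figure of its own to reproduce.

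**Inputs from the document.** 9 v 9 players (Participants); two collection moments (Interventions); p < 0.05 (Statistical analysis).

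**Assumptions.** ρ from 0.5 to 0.95; r = post SD/pre SD, taken as 1 unless stated; bivariate normal times; all 18 players with both measurements.

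**1. Identity.** With two measurements per player, the group-by-time F on (1, 16) df equals the square of the two-sample t on change scores. In a numerical 9 v 9 example, F = t² = 3.1824, with p = 0.0934 both ways. With more than two measurements per player this identity does not apply as it stands.

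**2. What stays in the estimate.** Let D be the pre-test difference (experimental minus control, in pre-test SDs) and τ the true effect.
- Change score: E[estimate | D] = τ − (1 − ρr)D.
- ANCOVA: E[estimate | D] = τ.

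At r = 1 and D = 0.5, the shift is 0.5(1 − ρ): 0.25, 0.15, 0.10, 0.05 and 0.025 SD at ρ = 0.5, 0.7, 0.8, 0.9 and 0.95. At r = 1.25 and ρ = 0.8, the share is 1 − 0.8 × 1.25 = 0. At r = 1.25 and ρ = 0.95, it is 1 − 0.95 × 1.25 = −0.19, so the direction reverses.

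**3. How often imbalance arises.** The SE of D is √(2/9) = 0.471 SD. P(|D| > 0.5) = 2(1 − Φ(0.5/0.471)) = 0.289. The 0.5 SD cut-off is this review's choice.

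**4. False-positive rates at r = 1** (%, two-sided; 1,000,000 simulated trials per ρ; figures good to about 0.1 point):

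| ρ | 0.5 | 0.7 | 0.8 | 0.9 | 0.95 |
|---|---|---|---|---|---|
| Planned test, D beyond ±0.5 SD | 9.1 | 7.5 | 6.6 | 5.8 | 5.4 |
| Planned test, D within ±0.5 SD | 3.3 | 4.0 | 4.3 | 4.6 | 4.8 |
| Planned test, all allocations | 5.0 | 5.0 | 5.0 | 5.0 | 5.0 |

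ANCOVA gives 4.9 to 5.1% in both subsets. Check that the subsets average to 5%: at ρ = 0.5, 0.289 × 9.07 + 0.711 × 3.34 = 5.0; at ρ = 0.8, 0.289 × 6.64 + 0.711 × 4.30 = 5.0.

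**5. Precision.** Variance ratio ANCOVA/change = r²(1 − ρ²)(15/14)/(r² + 1 − 2ρr).
- r = 1: this reduces to (1 + ρ)/2 × 15/14 = 0.804, 0.911, 0.964, 1.018 and 1.045 at the five values of ρ. Break-even is at ρ = 28/15 − 1 = 0.867.
- r = 0.8: 0.56 to 0.69 over ρ = 0.5 to 0.95.
- r = 1.25: 0.87 to 1.07; ANCOVA is less precise for ρ of about 0.58 to 0.91.

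The largest possible ratio is 15/14 = 1.07, reached when ρr = 1, where the change score already uses the right slope. Then √1.07 = 1.035, so the CI is about 3 to 4% wider.

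**6. Power at r = 1, change v ANCOVA.** For a 1 SD effect: 51 v 60% at ρ = 0.5 and 88 v 89% at ρ = 0.8. For a 0.5 SD effect: 61 v 60% at ρ = 0.9.

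**The case against.** The strongest reply is that no defect has been shown. A mixed ANOVA is a legitimate analysis of a randomised pre/post design, its overall type I error is 5%, and at ρ of 0.8 to 0.95 with equal SDs the choice moves power by about one point either way. All of that stands, and it is why this is a recommendation and not a correction.

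The tail rates can also be made to sound worse than they are. At a difference of exactly 0.5 SD, the planned test's false-positive rate is only 5.2% (ρ = 0.5) or 5.1% (ρ = 0.8 and 0.9). The averages in the table are driven by larger imbalances: above 0.75 SD in about 11% of allocations and above 1 SD in about 3%. Since neither ρ nor r is in the documents, the size and even the sign of the retained share rest on assumption.

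ANCOVA has conditions of its own. Its conditional error rate relies on a common linear slope, which nine players per group can test only weakly.

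What survives is narrower. For the one allocation that occurs, ANCOVA's error rate stays near 5% whatever ρ and r are, given that slope assumption; the planned test's does so only if the imbalance happens to be unimportant.

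**Conclusion.** The point holds as a cheap improvement to a valid plan. Its basis is validity given the allocation obtained, not precision. If r = 1, the planned test's average false-positive rate in the roughly 29% of allocations with a pre-test difference above 0.5 SD runs from 9.1% (ρ = 0.5) down to 5.4% (ρ = 0.95), balanced by rates below 5% in the rest.

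Three stronger readings are tempting and are not supported:
- That the planned analysis is invalid or favours the experimental group. Allocation is random, so imbalance falls either way and the overall error rate is 5%.
- That ANCOVA will be more precise. This depends on ρ and r, and the 0.867 break-even applies only at r = 1.
- That the group that starts slower always benefits. This reverses when ρr exceeds 1.

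All figures assume two measurements per player. If Trial Design means testing around the warm-up at both moments, they do not carry over directly.

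**What to change.** 1. State how many measurements each player has, reconciling Trial Design with Interventions, and say which is the pre-test and which the post-test.
2. For the change-of-direction T-test and for the 40-m sprint, fit post-test time = group + pre-test time. Report the adjusted between-group difference in seconds with its 95% CI as that outcome's test of the hypothesis in the Introduction.
3. Plot post-test against pre-test by group as a descriptive check of the common slope, and say in advance that the plot does not change the main model.
4. Keep the mixed ANOVA's group-by-time result, named as such, as a sensitivity analysis.

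The cost is wording in the analysis section: the data are already planned and the model is a standard SPSS procedure. The statistical price is one residual degree of freedom (15 instead of 16), the common linear slope assumption, and at worst about 7% more variance (CI about 3 to 4% wider).

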PAP is associated to an increase in contractile muscle force, in response to maximal voluntary contractions and capable of conditioning subsequent muscle contractions, measured as the maximal contraction force evoked by supramaximal electrical stimulation (Blazevich & Babault, 2019; Prieske et al., 2020). From a physiological perspective, the main mechanism of PAP is the phosphorylation of myosin regulatory light chains (Blazevich & Babault, 2019; Boullosa et al., 2018; Prieske et al., 2020; Tillin & Bishop, 2009). The authors suggest that there is a time window to optimize the PAP, with a recovery period between 7 to 10 minutes (Wilson et al., 2013).

Conversely, PAPE refers to the increase in maximal voluntary strength, power, or velocity (dynamic or isometric) following a conditioning contraction (Prieske et al., 2020). Accordingly, different training protocols have been used to improve the PAPE, such as PLY (Brink et al., 2022), resistance training (Carbone et al., 2020), sprint training (Bevan et al., 2010), the flywheel paradigm (Sañudo et al., 2020) and COD drills (Lockie et al., 2014). Similarly to PAP, the performance enhancing effects may be observed after a resting period, peaking 7-10 minutes after a conditioning contraction (Cuenca-Fernández et al., 2017; Maloney et al., 2014; Tillin & Bishop, 2009; Wilson et al., 2013).

The effectiveness by which a conditioning activity can stimulate the mechanisms that strengthen muscles and improve performance depends on the balance between fatigue and potentiation (Rassier & Macintosh, 2000; Tillin & Bishop, 2009; Wilson et al., 2013). This balance is affected by a variety of factors, including training experience (Prieske et al., 2020),

resting time using an optimal recovery time (Hodgson et al., 2005; Tillin & Bishop, 2009), the intensity of the conditioning activity performed (Sale, 2002), muscle fiber type and gender (DeRenne, 2010). Therefore, optimal performance occurs when fatigue has decreased, and the potentiated effect still exists (Hodgson et al., 2005). Therefore, this study aims to determine if the performance of female football players is affected after the exposure to a potentiation protocol. It is hypothesized that performance in the selected physical tests will improve significantly and meaningfully after performing the chosen potentiation protocol compared to the control group's warm-up.

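### With nine players per group every significant result is labelled 'large', and no confidence interval for the between-group difference in change is planned

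*Combined protocol and SAP*

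**What the plan says.** The Introduction hypothesises that performance in the chosen tests "will improve significantly and meaningfully after performing the chosen potentiation protocol", compared with the control group's warm-up. The Participants section states that "Eighteen female soccer players between 16 and 21 years of age will participate in this study", nine allocated to each group.

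The Statistical analysis section plans a mixed repeated measures ANOVA. It gives one rule for significance ("Statistical significance will be assumed at" p < 0.05) and one measure of size, partial eta squared, whose values "will be classified as small (0.010-0.059), moderate (0.060-0.137), and large" above 0.137. It adds that "data will be presented by mean" and standard deviation. For the sprint, "The time will be counted in seconds and thousandths of a second"; the T-test uses the same photocell system.

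The plan contains no confidence interval, no between-group difference in seconds, and no statement of how large an improvement must be to count as meaningful. It does not connect the eta squared labels to the word 'meaningfully'.

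**The concern.** The hypothesis makes two claims, one about significance and one about size. A reader looking for the second will find only the eta squared labels. If those labels cannot vary among significant results, they cannot help to answer it. Partial eta squared is also scaled by the variability of the players' change scores, so the same label can stand for quite different gains in seconds. A coach choosing between warm-ups needs to know how many seconds were gained and how precisely that is known. The planned output does not show that precision directly.

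**Working it through.** **Inputs.** Eighteen players, 9 + 9 (Participants). Two test occasions: Trial Design describes testing before and after, and Interventions describes two collection moments. Significance at p < 0.05 and the label cut-offs come from Statistical analysis. The plan states no power, target difference or SD, so there is no figure of its own to reproduce.

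**Step 1: the test.** With two groups and two occasions, the group-by-time F equals the square of the two-sample t on the change scores, with 1 and N − 2 degrees of freedom. Hence partial eta squared = F / (F + N − 2). At N = 18 this is F / (F + 16).

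**Step 2: the 'large' cut-off as a p-value.** At 0.137, F = 16 × 0.137 / 0.863 = 2.540, which gives p = 0.131.

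**Step 3: what significance requires, and the width of the missing interval.** The half-width of the 95% CI for the difference in mean change is t × √(1/n₁ + 1/n₂) × SD of change, where t is the square root of the critical F.

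| Analysed | Critical F | Smallest partial eta squared with p < 0.05 | Half-width, in SD of change |
|---|---|---|---|
| 18 (9 + 9) | 4.494 | 4.494 / 20.494 = 0.219 | 2.120 × √(2/9) = 1.00 |
| 16 (8 + 8) | 4.600 | 4.600 / 18.600 = 0.247 | 2.145 × √(2/8) = 1.07 |
| 14 (7 + 7) | 4.747 | 4.747 / 16.747 = 0.283 | 2.179 × √(2/7) = 1.16 |

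In every row the value needed for significance exceeds 0.137, so a significant 'small' or 'moderate' result is impossible. Loss of players widens the gap. The overlap would end only at 29 players: the value needed is 0.140 at 28 and 0.135 at 29.

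**Step 4: the one-way nature of the overlap.** Significant implies 'large', but 'large' does not imply significant: values above 0.137 and below 0.219 are 'large' with p between 0.05 and 0.13.

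**Step 5: the interval in seconds.** The documents give no SD of change. Over an assumed range of 0.05 to 0.30 s, the half-width with 18 players is about 0.05 to 0.30 s.

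**The case against.** Several stronger readings are tempting, and the documents do not support them.

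- *A reader might infer that the plan uses the label as its test of 'meaningfully'.* It does not say so. The labels are a cited convention, reporting them is not an error, and no pass/fail rule is attached to them. What stands is that the hypothesis uses a word for which the plan supplies no criterion.
- *A reader might infer that results of very different strength could not be told apart.* At 18 players, p = 0.05 gives partial eta squared of 0.219 and p = 0.001 gives 0.502. Both are 'large', but the planned eta squared value and p-value already separate them.
- *A reader might infer that direction is lost.* The label has no direction, but the planned group means show it.
- *A reader might worry about non-significant results labelled 'moderate' or 'large'.* The hypothesis asks for significance as well, so it does not call for reading the labels alone.

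It is also fair to say that effect size tracks p at any fixed sample size, and that the overlap arises mainly because there are nine players per group. That is correct. The specific point is that, at this size, the chosen bands do not distinguish among significant results.

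Finally, a reader could rebuild the interval, because the standard error is |difference| / √F and F = 16 × eta squared / (1 − eta squared). Near the significance boundary this works well: a value rounded to 0.22 (0.215 to 0.225) gives a standard error of 0.478 to 0.464 times the difference. For a value rounded to 0.01 (0.005 to 0.015) the range is 3.53 to 2.03 times the difference, a factor of 1.7. So nothing is lost from the data, but readers should not have to reconstruct the interval.

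**Conclusion.** The point holds as a gap in reporting and interpretation. With 18 players analysed and two occasions, every significant group-by-time result is labelled 'large', because significance needs at least 0.219 and the label starts at 0.137. This is exact for the planned two-by-two model and needs no assumed SD or effect; it holds equally with 16 or 14 players. The label therefore adds no information on size beyond the p-value, and no interval for the difference in change is planned to supply it.

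The finding does not show that the planned test is invalid, that data are lost, or that the plan has adopted a faulty rule for 'meaningfully'. The change is worth making because it costs almost nothing and bears directly on the trial's own hypothesis.

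**What to change.** In the Statistical analysis section, for the T-test and the 40-m sprint, plan to report the between-group difference in pre-to-post change in seconds with its 95% CI. Base statements about the size of the improvement on that interval and not on the eta squared labels. Partial eta squared and its labels may still be reported.

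A secondary step applies only if the team wants to claim a meaningful improvement. It should then state, before testing, the difference in seconds it will use and whether the point estimate or the whole interval must exceed it. The documents give no value for this difference and none is proposed here.

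The first change takes a sentence or two, needs no new data, and leaves the test and p-value as they are. The second costs more, because the difference must be justified for each test. The downside of the interval is candour: with a half-width of about 1.0 SD of the change scores, many results will read as inconclusive.

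### Two unranked outcomes and no stated success rule: does this inflate the trial's false-positive rate?

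*Combined protocol and SAP*

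**What the plan says.** The Introduction states one directional hypothesis: "performance in the selected physical tests will improve significantly and meaningfully", and this is to occur "after performing the chosen potentiation protocol compared to the control" group's usual warm-up. The Outcomes section then describes two measurements under separate subheadings. For the first, "Pre-planned COD will be assessed through the T-test". For the second, the same photocell system "will be used for the 40-linear sprint". Neither is ranked above the other.

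Under Statistical analysis, "a mixed repeated measures ANOVA (i.e., within- and between-factors) will be used", and "Statistical significance will be assumed at" p < 0.05. That section gives no primary outcome, no rule for combining the two tests and no multiplicity adjustment.

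On timing, Trial Design says "Each group will be tested before and after performing the WU to which they are assigned". Interventions puts the first collection at the start of the first session of week two and "the second moment at the end of the third week". The analysis therefore has two measurement occasions, and the contrast that matches the hypothesis is group by time.

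**The concern.** One hypothesis, two tests of it and one unadjusted threshold is the usual setting for multiplicity. If a significant result on either test were taken to confirm the hypothesis, the trial would have two chances of a false success. With no rule written in advance, that reading could be chosen after the results are known. The assessors are also unblinded, which makes rules fixed beforehand more attractive. At stake is whether the 5% threshold (2.5% in the direction of benefit) describes the error rate of the trial's overall conclusion.

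**Working it through.** The documents give no power, sample-size or family-wise error figure, so there is nothing of the plan's own to reproduce.

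**Inputs from the documents.** Threshold 0.05 per test (Statistical analysis); two outcomes (Outcomes); 9 players per group (Participants); two occasions (Trial Design, Interventions).

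**Inputs assumed.** The correlation ρ between the two change scores, varied from 0 to 0.95. For power: pre-post correlation r and a true effect in SDs of a single-occasion score.

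**Step 1: one outcome.** With two occasions, the group-by-time F test is the square of a t test on change scores with 9 + 9 − 2 = 16 df. It is non-directional, so the error in favour of the intervention is 0.05 / 2 = 2.5%.

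**Step 2: either outcome is enough.** For ρ = 0 the error in favour is 1 − 0.975² = 4.94%, and in any direction 1 − 0.95² = 9.75%. For ρ > 0 the normal-model error in favour is 1 − Φ₂(1.96, 1.96; ρ), where Φ₂ is the bivariate normal distribution function. Simulated t tests with 9 per arm (400,000 to 2 million null trials per value) check the small-sample case.

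| ρ (assumed) | Either, normal model | Either, simulated | Both, simulated |
|---|---|---|---|
| 0 | 4.94% | 4.93% | 0.06% |
| 0.5 | 4.54% | 4.67% | 0.4% |
| 0.8 | 3.90% | 3.95% | 1.0% |
| 0.9 | 3.52% | 3.57% | 1.4% |
| 0.95 | 3.23% | 3.28% | 1.8% |

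The excess over 2.5% therefore runs from 3.3 − 2.5 = 0.8 to 4.9 − 2.5 = 2.4 percentage points. At ρ = 0.3 the normal model gives 4.76%, so the range for ρ from 0.3 to 0.8 is 3.9% to 4.8%.

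**Step 3: the other two readings.**
- *Both required.* With no effect on either test, the error is the last column of the table. If one test has a true effect and the other has none, a joint success still needs a false positive on the null test, so the error cannot exceed 2.5%.
- *Separate conclusions.* Each claim keeps its own 2.5%.

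**Step 4: what formal control would cost.** Power per outcome is shown for the same true effect on both tests and ρ = 0.5, at r = 0.5 / 0.7 / 0.8 (all assumed). Unadjusted values are from the noncentral t with noncentrality δ / [√(2(1 − r)) × √(2/9)]. For example, δ = 0.5 and r = 0.5 give 0.5 / (1 × 0.471) = 1.06 and power 16.8%. The other rows are simulated.

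| Rule | 0.5 SD | 1.0 SD |
|---|---|---|
| Unadjusted | 16.8 / 25.1 / 35.1% | 51.3 / 73.0 / 88.2% |
| Second outcome in a fixed sequence | 6.5 / 11.7 / 19.2% | 34.0 / 58.9 / 80.4% |
| Holm, each outcome | 11.6 / 18.7 / 27.7% | 43.8 / 67.5 / 85.6% |

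At 0.5 SD and r = 0.5, the fixed sequence leaves the second outcome with 6.5 / 16.8 = 39% of its unadjusted power. Holm leaves each outcome with 11.6 / 16.8 = 69%.

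**The case for a change.** The strongest case for a change is that the missing rule decides the answer. For a true effect of 0.5 SD on both tests, with r = 0.7 and ρ = 0.5 (all assumed), the chance of declaring success is about 39% if either test is enough and 12% if both are needed. The same data could then be reported as supporting the hypothesis or not. The Introduction states one hypothesis rather than two, so separate conclusions are not declared either. Writing a rule takes two or three sentences, and naming a primary outcome costs that outcome no power.

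Much of this stands. The rule is unwritten, the figures are right, and a sentence in the analysis section would be tidier. What does not follow is that the planned analysis is wrong. The hypothesis speaks of the selected tests in the plural, with no suggestion that one of them is enough. The two tests measure different qualities, change of direction and straight-line speed, so reporting each on its own result is natural. The reader will see both results and can tell a finding on one test from a finding on both.

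A similar worry is that a mixed ANOVA yields three effects per outcome. The stated comparison with control, with testing before and after, already points to group by time.

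**Conclusion.** No change is needed. The plan leaves out a success rule, and analysts fill that gap sensibly by running one ANOVA per test, reading the group-by-time effect and drawing a conclusion for each test. Those per-outcome conclusions hold at the stated level.

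The inflation arises only if one significant test is announced as confirming the whole hypothesis, which no section says. Even then the error in favour is about 3.9% to 4.8% for ρ from 0.3 to 0.8, and 3.3% to 4.9% over the wider range of 0 to 0.95, against 2.5%. These figures rest on two measurement occasions, a two-sided reading of p < 0.05 and a change-score correlation that the documents do not give.

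Formal control is a debatable trade in an 18-player convenience sample. It would lower a modest, conditional error by taking power from tests that have little, and the documents give no basis for ranking one test above the other. A report that gives both results and does not present one significant test as proof of the overall hypothesis stays within what the design supports.
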